### **Exploratory endpoints**

SARS-CoV-2 viral load measures will be assessed using a linear mixed effects model, with fixed effects of time, baseline viral load, age, BMI, and days of symptoms at time of enrollment, and a random effect for participant. The measures may be transformed to satisfy the normality assumption needed for the linear mixed effects model fit. Mean viral concentrations will be summarized by treatment group and compared over time based on the model fit.

Viral sequencing may be used to assess the phylogenetic relationships between SARS-CoV-2 viruses obtained from positive nasal swab samples. Phylogenetic trees will be generated to determine whether participants were part of a transmission cluster.

#### **10.5.2. Safety Analyses**

Safety analyses will be conducted in the safety population.

The proportion of participants with Grade 3 AEs, Grade 4 AEs, AEs resulting in study intervention discontinuation, and SAEs will be summarized by treatment group, with 95% exact CIs.

In addition, reported AESIs will be summarized overall and by group.

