**Table 3: Objectives and Endpoints**

Objectives	Endpoints
Primary	
To characterize safety of study intervention	
Through Day 35
 
 
• Frequencies of grade 3 AEs and grade 4 AEs
 
• AEs resulting in study intervention discontinuation
 
• All SAEs
 

To assess efficacy of study intervention	
 
• Proportion of participants who progress to moderate or severe disease category or higher (Gates MRI ordinal scale <math>\geq 3</math>) through Day 28
 

Secondary	
To assess clinical efficacy of study intervention	
 
• Time to disease resolution, defined as BOTH viral clearance (two consecutive negative diagnostic tests) and symptoms resolution (new onset COVID-19 symptoms resolved, and pre-existing symptoms returned to baseline*) through Day 28
 
• Time to disease resolution, defined as symptoms resolution only (new onset COVID-19 symptoms resolved, and pre-existing symptoms returned to baseline*) through Day 28
 
• Proportion of participants who progress to moderate or severe disease category or higher (Gates MRI ordinal scale <math>\geq 3</math>) at Days 8, 14 and 21
 
• Proportion of participants who achieve disease resolution at Days 8, 14, 21 and 28
 
• Gates MRI scale score at Days 8, 14, 21 and 28
 
• WHO ordinal scale score at Days 8, 14, 21 and 28
 
• Incidence and number of days of hospitalization at Days 8, 14, 21 and 28
 

Exploratory objectives	
To assess virological efficacy	
 
• Quantity (and change from baseline) of SARS-CoV-2 virus at Days 8, 14, 21 and 28
 

To assess viral sequence	
 
• Phylogenetic relationships of SARS-CoV-2 viruses sequenced from positive nasal swab samples
 

\*Baseline refers to health status prior to contracting COVID-19.

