## 5. Study Design

### 5.1. Overall Design

This is a randomized, controlled study for treatment of mild COVID-19 in people at high risk for disease progression.

Mild COVID-19 is determined by Gates MRI mild COVID-19 clinical endpoint definition (refer to [Table 7](#)).

High risk is defined based on age, BMI or presence of a comorbidity.

**Primary purpose:** To assess the safety and clinical efficacy of rivaroxaban in reducing the proportion of participants who have progressed to moderate or severe disease category or higher in people with mild COVID-19 who are at increased risk of disease progression.

**Interventional model:** Participants will be randomized 1:1 to either the rivaroxaban or the placebo group, in parallel for the duration of the study. Randomization will be stratified by site and by number of days since onset of symptoms (<6 days vs.  $\geq 6$  days).

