#### Safety

With 300 participants in the rivaroxaban intervention group, there is 80% probability to observe at least one SAE related to rivaroxaban when the true SAE rate is at least 0.54%.

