**Figure 3: Randomization strategy for sites where 3 interventions are being studied**

**Figure 4: Randomization strategy for sites where 2 interventions are being studied**

**Figure 5: Randomization strategy for sites where only 1 intervention is being studied**

#### 10.4. Primary and Key Secondary Endpoints

The primary efficacy endpoint is the proportion of participants who progress to moderate or severe disease category or higher (Gates MRI ordinal scale  $\geq 3$ ) through Day 28.

Secondary efficacy endpoints include time to disease resolution, defined as symptoms resolution with or without viral clearance, proportion of participants with disease resolution, Gates MRI and WHO ordinal scales, and incidence and duration of hospitalization.

Primary safety endpoints include the frequency of Grade 3 and Grade 4 AEs, AEs resulting in study intervention discontinuation and SAEs.

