### 10.5.1. Efficacy Analyses

#### **Primary efficacy endpoints**

The primary efficacy analysis will be conducted in the ITT population. Within the rivaroxaban analysis population as defined in [Section 10.3.1](#), participants randomized to rivaroxaban will be compared to participants randomized to placebo/standard of care.

The proportion of participants who progress to moderate or severe disease category or greater through Day 28 will be summarized by treatment group. The absolute difference in the risk of progression to moderate or severe disease category or greater will be assessed using the stratified Miettinen and Nurminen method to compare the difference between two rates [[Miettinen 1985](#)].

Sensitivity analyses will be repeated as described above using the mITT and PP populations, to assess the robustness of the primary results.

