12.1 Adverse Events

AEs will be coded using MedDRA version 22.1 or higher. AE severity will be graded as Grade 1 (Mild), Grade 2 (Moderate), Grade 3 (Severe), Grade 4 (Potentially Life-threatening), or Grade 5 (Death) as referencing to the specific toxicity grading by Division of Acquired Immunodeficiency Syndrome (DAIDS) AE Grading Table [[DAIDS 2017](#)].

AEs starting on or after first day of study intervention will be considered as treatment-emergent. Only AEs within the reporting window will be included within the relevant category in summary tables. All AEs will be listed, regardless of if it was reported within the applicable reporting window.

An AE overview table containing the frequency and percent of participants in each of the following categories (summarized by intervention group) and also the 95% CI (calculated for a single proportion using the Mid-p method):

- Any AE
- Related AEs
- Grade 3 AEs
- Grade 4 AEs
- AEs resulting in study intervention discontinuation
- SAEs
- AEs with outcome of death
- AESIs (including major bleeding and severe hypersensitivity to rivaroxaban)

Additionally, the following will be summarized by SOC and PT for each intervention group:

- Incidence of AEs
- Incidence of related AEs

- Incidence of Grade 3 AEs
- Incidence of Grade 4 AEs
- Incidence of AEs resulting in study intervention discontinuation
- Incidence of SAEs
- Incidence of AEs with outcome of death
- Incidence of AESIs

Summaries of SOC and PT will be sorted alphabetically by SOC and by decreasing frequency of PT in the intervention group. If a participant has more than 1 AE at a given level (e.g., SOC and PT), the participant will only be counted once within that level.

Missing severities and relationship will not be regarded as ‘worst case’.

Incidences of Grade 3 AEs, Grade 4 AEs, and AEs resulting in study intervention discontinuation will be summarized by subgroups.

- Race (white, black, other)
- Ethnicity (Hispanic or Latino, Not Hispanic or Latino)
- Sex (male, female)
- Number of days since onset of symptoms at time of randomization (<6 days or ≥6 days)
- Presence of comorbidities/risks
 - Age (<65 years, ≥65 years)
 - Presence of chronic pulmonary disease, COPD, pulmonary hypertension (Yes, No)
 - Diabetes mellitus (type 1 or type 2) requiring medication or insulin (Yes, No)
 - Hypertension, requiring at least 1 oral medication for intervention (Yes, No)
 - Immunocompromised status due to disease or medication (Yes, No)

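### The primary safety endpoints and AESIs are reported arm by arm, with no planned rivaroxaban-minus-placebo estimate

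*Protocol*

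**What the plan says.** Protocol Table 3 lists safety first among the primary objectives: "To characterize safety of study intervention". Protocol 10.4 names the endpoints: "Primary safety endpoints include the frequency of Grade 3 and Grade 4 AEs, AEs resulting in study intervention discontinuation and SAEs". The design is parallel and placebo-controlled (Protocol 5.1): "Participants will be randomized 1:1 to either the rivaroxaban or the placebo group".

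The planned safety analysis stays within each arm:

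- Protocol 10.5.2: Grade 3 AEs, Grade 4 AEs, "AEs resulting in study intervention discontinuation, and SAEs will be summarized by treatment group, with 95% exact CIs". For AESIs: "In addition, reported AESIs will be summarized overall and by group".
- SAP 12.1: an overview table by intervention group with a "95% CI (calculated for a single proportion using the Mid-p method", followed by incidence tables by system organ class, preferred term and subgroup. The overview table has an AESI row.

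The efficacy analysis, in contrast, compares the arms. Progression is assessed with the "stratified Miettinen and Nurminen method to compare the difference between two rates" (Protocol 10.5.1). SAP 11.1.1 writes the method out in full, stratified by days since symptom onset. SAP 11.2.3 uses the same method for disease resolution, and SAP 11.2.7 gives a stratified risk ratio with CI for hospitalization.

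**The concern.** Participants have acute COVID-19 and are at raised risk of progression; the sample size assumes that 30% of controls progress. SAEs and Grade 3 or 4 events will therefore arise in both arms whatever rivaroxaban does. A rate in the rivaroxaban arm with its own interval mixes disease and drug. What the drug adds is the difference from placebo.

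As written, the planned output for a primary objective contains no excess risk and no interval for it. The report would therefore not say how large an excess the data are compatible with, or how large an excess they make unlikely. A reader left with two intervals may take their overlap as a sign of no difference, and that inference is unreliable.

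**Working it through.** **1. The plan's own safety figure.** Protocol 10.1 and SAP 9.1.2 state that with 300 on rivaroxaban "there is 80% probability to observe at least one SAE related to rivaroxaban when the true SAE rate is at least 0.54"%. Check: 1 − (1 − 0.0054)^300 = 0.803. The figure reproduces. It describes one arm only and is not in dispute.

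**2. What is and is not compared between arms.**

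- Death and hospitalization are both SAE criteria (Protocol 9.5.3). Both count as progression in the primary risk difference (SAP 11.1.1), and hospitalization also gets a risk ratio (SAP 11.2.7). These estimates run through Day 28 and use the efficacy set that SAP 7.1 defines after the early stop.
- No between-arm estimate is planned for total SAEs, Grade 3 AEs, Grade 4 AEs, AEs leading to discontinuation, AESIs, or any safety event on Days 29 to 35.

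**3. Why two intervals are not an interval for the difference.** The documents give no expected AE rates by arm, so the counts here are assumptions: 18/300 (6.0%) on rivaroxaban and 6/300 (2.0%) on placebo.

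- Per-arm standard errors: √(0.06 × 0.94/300) = 1.37 points and √(0.02 × 0.98/300) = 0.81 points.
- Simple normal intervals stop overlapping only when the rates differ by more than 1.96 × (1.37 + 0.81) = 4.27 points.
- The standard error of the difference is √(1.37² + 0.81²) = 1.59 points, so its interval excludes 0 from 1.96 × 1.59 = 3.12 points. The observed 4.0 points lies between the two thresholds.

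With the methods that the documents name:

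| | Rivaroxaban 18/300 | Placebo 6/300 | Overlap? |
|---|---|---|---|
| Exact 95% CI (Protocol) | 3.59 to 9.32% | 0.74 to 4.30% | yes |
| Mid-p 95% CI (SAP) | 3.71 to 9.14% | 0.81 to 4.11% | yes |

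The Miettinen-Nurminen score statistic at a difference of 0 (unstratified here) uses the pooled rate 24/600 = 0.04:

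- Variance = (600/599) × 2 × 0.04 × 0.96/300 = 0.0002564, so SE = 0.01601.
- Z = 0.04/0.01601 = 2.50.
- Inverting the score test gives a difference of 4.0 points, 95% CI 0.93 to 7.51. Fisher's exact p = 0.020.

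**4. Is this one lucky example?** For a range of assumed placebo counts at 300 per arm, the table gives the smallest rivaroxaban count at which each display shows a separation.

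| Placebo events | Difference CI excludes 0 from | Exact CIs disjoint from | Mid-p CIs disjoint from |
|---|---|---|---|
| 3 | 10 | 16 | 15 |
| 6 | 15 | 21 | 20 |
| 9 | 20 | 26 | 25 |
| 15 | 28 | 35 | 34 |
| 30 | 46 | 55 | 54 |

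The gap is about 5 to 9 events throughout. At an assumed 200 per arm with 6 placebo events the counts are again 15, 21 and 20. At the lower edge of each band the evidence is borderline (15 vs 6 of 300 gives Fisher p = 0.073), which is why 18 vs 6 is used above.

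**The case against.** The strongest reply is that the plan fits its objective. Safety is to be characterized, the only stated hypothesis concerns efficacy, and incidence by arm with intervals is a coherent descriptive plan. That stands: neither a formal test nor a powered safety comparison is owed.

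Several stronger readings are tempting and are not supported:

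- *Harm will be judged by whether intervals overlap.* Neither document adopts such a rule. The calculation shows what separate intervals fail to convey, not a decision error built into the plan.
- *The excess risk cannot be known.* Counts and percentages by arm are tabulated, so a reader can derive a difference and its interval. What is missing is a planned, reported estimate.
- *No harm outcome is compared between arms.* Death and hospitalization are, through Day 28, as efficacy outcomes.
- *The safety sample-size statement is wrong.* It reproduces, and it suits a trial that pauses on one related major bleed. Adding a two-arm precision statement would be a matter of preference.
- *The added estimate would be the strict randomized comparison.* The safety population is analysed by treatment received.

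The monthly unblinded safety review by the IDMC protects participants during the trial but puts no estimate in the report.

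The gain also has limits. For an assumed 2% vs 4% at 300 per arm, the difference CI excludes 0 in about 30% of trials. For an assumed 0.2% vs 0.9%, as might apply to a rare AESI, it does so in about 16%, and in about 7% at 200 per arm. The interval is still worth reporting, because its upper limit shows what excess remains compatible with the data.

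**Conclusion.** The point holds as a cheap improvement to reporting. A primary objective of a placebo-controlled trial lacks a planned between-arm estimate for total SAEs, Grade 3 and Grade 4 AEs, discontinuation AEs and AESIs, and for all safety events after Day 28. Efficacy proportions in the same plan do have one. Nothing in the plan is biased or contradictory on this account, and no data are lost.

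The size rests on illustration. In the worked case a 4.0-point excess (0.9 to 7.5) would appear only as two overlapping intervals. The event counts are assumed. So are the arm sizes: randomization stopped early on 4 February 2021 and the final numbers per arm are not given, so 200 to 300 per arm was used. The pattern is nearly the same across that range.

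**What to change.** In Protocol 10.5.2 and SAP 12.1, for each primary safety endpoint and for the AESI row of the overview table, add the rivaroxaban-minus-placebo risk difference with its Miettinen-Nurminen 95% CI. Stratify by days since symptom onset (<6 vs ≥6), as in SAP 11.1.1. Use the as-treated safety population through Day 35. Label the column as descriptive estimation without multiplicity control. Leave Protocol 10.1 and SAP 9.1.2 unchanged on safety.

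The cost is one column in existing tables, with a method the SAP already specifies and no new data or visits. The downside is several unadjusted intervals, which will be wide for rare AESIs; the label deals with the first, and the second is an honest display of what the trial can say.

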#### **10.6. Interim Analysis**

The primary analysis will occur after all participants complete Day 35. There will be 1 prespecified interim analysis to assess futility. If the trial does not cross the pre-specified boundaries to declare futility at the interim analysis, a final efficacy and safety analysis will occur after all participants complete the study Day 35 of follow-up.

A group sequential design strategy will be used to assess futility at the interim analysis. The interim analysis will occur after approximately 200 participants have completed Day 28 of follow-up. A Hwang-Shih-DeCani beta spending approach will be used [[Jennison 2000](#)]. The gamma parameter used will be -4, which is similar to the boundaries from the O'Brien-Fleming method [[O'Brien 1979](#)]. The lower bound for futility will be binding.

### **11. Operational Considerations**

#### **11.1. Independent Data Monitoring Committee**

An IDMC will be convened for this study with expertise in COVID-19 or respiratory viruses and emerging epidemics as well as biostatistics.

The purpose of the IDMC is to monitor the study for safety and efficacy. The IDMC may request additional information, or a pause in recruitment and dosing, while safety data are being evaluated.

The IDMC will operate according to a charter and the structure, participants, meeting information and other details will be provided in the charter. The charter will be available prior to study start.

The IDMC will meet monthly or ad hoc, if necessary, to review safety data, and may request additional information, or a pause, while safety data are being evaluated.

The IDMC will also review unblinded efficacy data at a pre-specified interim analysis. Pausing guidelines will apply (refer to [Section 6.6](#)).

All procedures associated with this review will be documented.

The IDMC will make a formal recommendation as needed.

The recommendations of the IDMC, along with the Sponsor's decision, will be communicated to the PIs and the IRBs/IECs and the national regulatory authorities as required. The Sponsor or its designee agrees to abide by any directives issued by the national regulatory authority or the IRB/IEC.

The IDMC will review the Pausing Guidelines ([Section 6.6 Study Pausing Guidelines](#)).

## **11.2. Informed Consent Process**

The PI or designee will explain the study to the participant and answer all questions regarding the study. The PI or designee will conduct the consent discussions on an individual basis with each participant. Adequate time will be allowed for all questions to be addressed. Potential participants will be interviewed to ensure that they meet all entry criteria relating to history.

Participants must be informed that their participation is voluntary. Participants will be required to sign a statement of informed consent that meets the requirements of FDA Code of Regulations (CFR) 21 CFR 50, local regulations, International Council for Harmonization of Technical Requirements for Pharmaceuticals for Human Use (ICH) guidelines, and the IRB/IEC or study center.

Written informed consent must be obtained before the participant is enrolled in the study, and the date the written consent was obtained must be documented. The authorized person obtaining the informed consent must also sign the ICF (see [Section 11.2.1](#)).

A copy of the ICF must be provided to the participant.

The intention for this study is that the consenting process will be conducted through remote/virtual contact and may use electronic consent functionality to obtain the participant's signature and date. Alternatively, an in-person visit may be conducted for consent if needed.

### **11.2.1. Informed Consent Forms**

The study ICF contains a section that addresses the use of remaining mandatory samples for research not described in the protocol, e.g., assay development and assay quality control.

Participants will be told that they are free to refuse to participate and may withdraw their consent at any time and for any reason during the storage period. Any test results from the samples collected before withdrawing consent may still be used for the study.

### **11.3. Data Protection**

Participants will be assigned a unique identifier by the Sponsor. Any participant record or dataset that is transferred to the Sponsor will contain the identifier only; participant names or any information which would make the participant identifiable will not be transferred to the Sponsor.

The participant must be informed that the participant's study-related data will be used by the Sponsor in accordance with local data protection law. The level of data disclosure must also be explained to the participant.

The participant must be informed that the participant's medical records may be examined by Clinical Quality Assurance auditors or other authorized personnel appointed by the Sponsor, by appropriate IRB/IEC members, and by inspectors from regulatory authorities.

### **11.4. Sample Retention and Future Use of Collected Biospecimen**

Biospecimens collected during the study will be retained securely for up to 10 years.

Collected biospecimens may also be used for future research. In addition, and only with the explicit and optional consent of study participants, samples or partial sample volumes that remain once a protocol-defined assay has been completed, may be stored and used for purposes other than protocol-related endpoints. Such "future research studies" would include, but not be limited to, assay development, assay quality control and development of methods related to COVID-19 research.

Biospecimens may be shared with research partners for scientific research purposes. Samples will not be sold, loaned, or given to any other independent groups for their own use. Research partners working with the Sponsor are not allowed to share samples with anyone who is not authorized by the Sponsor. The Sponsor will control what is done with all biospecimens.

### **11.5. Dissemination of Clinical Study Data**

Study information from this protocol will be posted on publicly available clinical trials registers (for example, clinicaltrials.gov) before enrollment of participants begins. Summaries of the results of the study will also be posted on the same website.

The final CSR will include all available data through the final study visit. The database will be locked prior to preparation of the final CSR when all of the above data have been entered, reviewed, and all queries related to the data have been addressed.

Modifications or additions to the analyses will be included in the relevant SAP. Any decisions to deviate from the planned analyses described in the protocol and in the SAP will be described in detail in the final CSR. The CSR will be reviewed and approved by the Sponsor signatory and the lead PI.

## **11.6. Data Quality Assurance**

All participant data relating to the study will be recorded on a printed CRF or, by an electronic CRF (eCRF) using an Electronic Data Capture (EDC) system or transmitted to the Sponsor or designee electronically (e.g., laboratory data). The PI is responsible for verifying that data entries are accurate and correct by physically signing or electronically signing the CRF.

The PI must maintain accurate documentation that supports the information entered in the CRF/eCRF.

The study will be monitored regularly by the Sponsor or its designee throughout the study period. The PI must permit study-related monitoring, audits, IRB/IEC review, and regulatory agency inspections and provide direct access to source data documents.

Monitoring details describing strategy (e.g., risk-based initiatives in operations and quality such as Risk Management and Mitigation Strategies and Analytical Risk-Based Monitoring), methods, responsibilities and requirements, including handling of noncompliance issues and monitoring techniques (central, remote, or on-site monitoring) are provided in the Monitoring Plan. Remote monitoring is preferred in this study.

The Sponsor or designee is responsible checking the accuracy and completeness of the data reported in the CRFs and the consistency with the source documents. The Sponsor assumes accountability for actions delegated to other individuals (e.g., contract research organization [CRO]).

Study monitors will perform ongoing source data verification remotely to confirm that data entered into the CRF by authorized site personnel are accurate, complete, and verifiable from electronic source documents provided; that the safety and rights of participants are being protected; and that the study is being conducted in accordance with the currently approved protocol and any other study agreements, ICH GCP, and all applicable regulatory requirements.

